7.2 Serious adverse events

7.2.1 Definition of SAE

An SAE is defined as any adverse event which meets any one of the following criteria:

- is fatal or life-threatening
- results in persistent or significant disability/incapacity
- constitutes a congenital anomaly/birth defect
- requires inpatient hospitalization or prolongation of existing hospitalization, unless hospitalization is for:
 - routine treatment or monitoring of the studied indication, not associated with any deterioration in condition (specify what this includes)

- elective or pre-planned treatment for a pre-existing condition that is unrelated to the indication under study and has not worsened since signing the informed consent
- treatment on an emergency outpatient basis for an event not fulfilling any of the definitions of a SAE given above and not resulting in hospital admission
- social reasons and respite care in the absence of any deterioration in the patient's general condition
- is medically significant, e.g. defined as an event that jeopardizes the patient or may require medical or surgical intervention.

All malignant neoplasms will be assessed as serious under “medically significant” if other seriousness criteria are not met.

Life-threatening in the context of a SAE refers to a reaction in which the patient was at risk of death at the time of the reaction; it does not refer to a reaction that hypothetically might have caused death if it were more severe (please refer to Annex IV, ICH-E2D Guideline).

Medical and scientific judgment should be exercised in deciding whether other situations should be considered serious reactions, such as important medical events that might not be immediately life threatening or result in death or hospitalization but might jeopardize the patient or might require intervention to prevent one of the other outcomes listed above. Examples of such events are intensive treatment in an emergency room or at home for allergic bronchospasm, blood dyscrasias or convulsions that do not result in hospitalization or development of dependency or abuse (please refer to Annex IV, ICH-E2D Guideline).

Any suspected transmission via a medicinal product of an infectious agent is also considered a serious adverse reaction.

7.2.2 SAE reporting

To ensure patient safety, every SAE must be reported to Novartis safety within 24 hours of learning of its occurrence.

All follow-up information for the SAE including information on complications, progression of the initial SAE and recurrent episodes must be reported as follow-up to the original episode within 24 hours of the investigator receiving the follow-up information. An SAE occurring at a different time interval or otherwise considered completely unrelated to a previously reported one must be reported separately as a new event.

Information about all SAEs is collected and recorded on the Serious Adverse Event Report Form; all applicable sections of the form must be completed in order to provide a clinically thorough report. The investigator must assess the relationship of each SAE to Secukinumab treatment or lifestyle intervention, complete the SAE Report Form in English, and submit the completed form within 24 hours to Novartis. Detailed instructions regarding the submission process and requirements for signature are to be found in the investigator folder provided to each site.

Follow-up information is submitted as instructed in the investigator folder. Each re-occurrence, complication, or progression of the original event must be reported as a follow-up to that event regardless of when it occurs. The follow-up information should describe whether the event has

resolved or continues, if and how it was treated, and whether the patient continued or withdrew from study participation.

SAE reporting in the Extension Period:

In the Extension Period, the treating physician is free to choose suitable psoriasis therapy for each patient.

Therapy with marketed Secukinumab or another Novartis product:

Any SAE occurring in the Extension Period should be notified to Novartis Patient Safety within 24 hours of learning of its occurrence, regardless of causality assessment.

Furthermore, any SAE occurring until 10 weeks (70 days) after the last study visit, or 12 Weeks (84 days) following the last administration of marketed Secukinumab, or 30 days after the subject has stopped study participation (whichever is later) must be reported to Novartis.

Also any non-serious adverse event needs to be documented in the Adverse Events CRF section during study participation.

Therapy with non-Novartis products:

Any SAE occurring in the Extension Period under therapy with a non-Novartis product is sent to Novartis Patient Safety regardless of causality, **within 12 weeks** after last administration of investigational drug Secukinumab or marketed Secukinumab (if switch is performed during the Extension Period). During the 12 weeks period, physician should clearly state on the SAE form which treatment (current non-Novartis therapy or previous Secukinumab treatment) has been assessed as suspected or not. After this 12 weeks period, only SAE need to be forwarded to Novartis for which causality was assessed as suspected for Secukinumab by investigator. Furthermore, any suspected SAE under a non-Novartis drug should be forwarded to the respective manufacturer or the regulatory authority by the investigator.

If the SAE is not previously documented in the Investigator's Brochure or Package Insert (new occurrence) and is thought to be related to the study treatment a Novartis Patient Safety Department associate may urgently require further information from the investigator for health authority reporting. Novartis may need to issue an Investigator Notification (IN) to inform all investigators involved in any study with the same study treatment that this SAE has been reported. Suspected Unexpected Serious Adverse Reactions (SUSARs) will be collected and reported to the competent authorities and relevant ethics committees in accordance with EU Guidance 2011/C 172/01 or as per national regulatory requirements in participating countries.

7.3 Liver safety monitoring

To ensure patient safety and enhance reliability in determining the hepatotoxic potential of an investigational drug, a standardized process for identification, monitoring and evaluation of liver events has to be followed.

The following two categories of abnormalities / adverse events have to be considered during the course of the study (irrespective of whether classified/reported as (S)AE):

- Liver laboratory triggers, which will require repeated assessments of the abnormal laboratory parameter
- Liver events, which will require close observation, follow-up monitoring and completion of the standard base liver CRF pages

Please refer to Table 14-1 in Appendix 2 for complete definitions of liver laboratory triggers and liver events.

Every liver laboratory trigger or liver event as defined in Table 14-1 of Appendix 2 should be followed up by the investigator or designated personal at the trial site as summarized below. Detailed information is outlined in Table 14-2 in Appendix 2.

For the liver laboratory trigger:

- Repeating the liver function test (LFT) within the next week to confirm elevation.

These LFT repeats must be performed using the central laboratory if possible. If this is not possible, then the repeats can be performed at a local laboratory to monitor the safety of the patient. Repeats laboratory must then be performed at central laboratory as soon as possible. If a liver event is subsequently reported, any local LFTs previously conducted that are associated with this event must be reported on the Liver CRF pages.

- If the elevation is confirmed, close observation of the patient will be initiated, including consideration of treatment interruption if deemed appropriate.

For the liver events:

- Repeating the LFT to confirm elevation as appropriate
- Discontinuation of the investigational drug if appropriate
- Hospitalization of the patient if appropriate
- A causality assessment of the liver event via exclusion of alternative causes (e.g., disease, co-medications)
- An investigation of the liver event which needs to be followed until resolution.

These investigations can include serology tests, imaging and pathology assessments, hepatologist's consultancy, based on investigator's discretion. All follow-up information, and the procedures performed must be recorded on appropriate CRF pages, including the liver event overview CRF pages.

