Treatment interruptions and dose adjustments of study treatment are **not** permitted. If a dose was not or incorrectly administered, this deviation must be recorded on the Dosage Administration Record CRF.

The same applies for the lifestyle intervention: Stopping participation (e.g. not showing up to counseling visits) or skipping counseling visits of the program is not permitted. Participation in the lifestyle intervention program must be recorded in the eCRF.

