Eosinophils: $> 1.1 \times \text{ULN}$

Lymphocytes: $> 1.1 \times \text{ULN}$

14 Appendix 2: Liver event definitions and follow-up requirements

Table 14.1 Liver Event Definitions

| | Definition/ threshold |
|--|--|
| Adverse event of special interest | |
| Laboratory values | ALT or AST $> 3 \times \text{ULN}$ ALP $> 2 \times \text{ULN}$ TBL $> 1.5 \times \text{ULN}$ |
| Medically significant event (SAE) | |
| Laboratory values | ALT or AST $> 5 \times \text{ULN}$ (with or without TBL $> 2 \times \text{ULN}$ [mainly conjugated fraction]) ALP $> 5 \times \text{ULN}$ (with or without TBL $> 2 \times \text{ULN}$ [mainly conjugated fraction]) TBL $> 3 \times \text{ULN}$ Potential Hy's Law cases (defined as ALT/AST $> 3 \times \text{ULN}$ and TBL $> 2 \times \text{ULN}$ [mainly conjugated fraction] without notable increase in ALP to $> 2 \times \text{ULN}$) |
| Adverse events | Any clinical event of jaundice (or equivalent term) ALT or AST $> 3 \times \text{ULN}$ accompanied by general malaise, fatigue, abdominal pain, nausea, or vomiting, or rash with eosinophilia Any event that links to a preferred term (PT) in the MedDRA dictionary falling under the SMQ sub-module "Drug-related hepatic disorders – severe events only"* or any "Hy's law case" PT |

* These events cover the following: hepatic failure, fibrosis and cirrhosis, and other liver damage-related conditions; the non-infectious hepatitis; the benign, malignant and unspecified liver neoplasms

Table 14-2 Liver Event Follow Up Requirements

| Criteria | Event type | Actions required | Follow-up monitoring |
|--|-----------------------|---|--|
| Potential Hy's Law case ^a | Medically significant | Discontinue the study drug immediately Hospitalize, if clinically appropriate Report to Novartis as an SAE Establish causality | ALT, AST, TBL, Alb, PT, ALP and γGT until resolution ^c (frequency at investigator discretion) |
| ALT or AST | | | |
| > 8 x ULN | Medically significant | Repeat LFT within 48 hours If elevation persists, discontinue the study drug immediately Hospitalize if clinically appropriate Report to Novartis as an SAE Establish causality | ALT, AST, TBL, Alb, PT, ALP and γGT until resolution ^c (frequency at investigator discretion) |

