| > 5 to ≤ 8 x ULN | Medically significant | Repeat LFT within 48 hours If elevation persists for more than 2 weeks , discontinue the study drug Report to Novartis as an SAE Establish causality | ALT, AST, TBL, Alb, PT, ALP and γGT until resolution ^c (frequency at investigator discretion) |
| > 3 x ULN accompanied by symptoms ^b | Medically significant | Discontinue the study drug immediately Hospitalize if clinically appropriate Report to Novartis as an SAE Establish causality | ALT, AST, TBL, Alb, PT, ALP and γGT until resolution ^c (frequency at investigator discretion) |
| > 3 to ≤ 5 x ULN (patient is asymptomatic) | AESI | Central laboratory to report to Investigator & Novartis Repeat LFT once or twice in the week If elevation persists, establish causality | Investigator discretion Monitor LFT within 1 to 4 weeks or at next visit |
| ≤ 3 x ULN (patient is asymptomatic) | N/A | Repeat LFT at next visit | |
| ALP (isolated) | | | |
| > 5 x ULN | Medically significant | Repeat LFT within 48 hours If elevation persists, report to Novartis as an SAE Establish causality | Investigator discretion Monitor LFT within 1 to 4 weeks or at next visit |
| > 2 to ≤ 5 x ULN (patient is asymptomatic) | AESI | Central laboratory to report to Investigator & Novartis | Investigator discretion Monitor LFT within 1 to 4 weeks or at next visit |

| Criteria | Event type | Actions required | Follow-up monitoring |
|--|-----------------------|---|--|
| | | Repeat LFT once or twice in the weekIf elevation persists, establish causality | |
| ≤ 2 x ULN (patient is asymptomatic) | N/A | Repeat LFT at next visit | |
| TBL (isolated) | | | |
| > 3 x ULN | Medically significant | Repeat LFT within 48 hours If elevation persists, discontinue the study drug immediately Hospitalize if clinically appropriate Report to Novartis as an SAE Establish causality | ALT, AST, TBL, Alb, PT, ALP and γGT until resolution ^c (frequency at investigator discretion) Test for hemolysis (e.g., reticulocytes, haptoglobin, unconjugated [indirect] bilirubin) |
| > 1.5 to ≤ 3 x ULN (patient is asymptomatic) | AESI | Central laboratory to report to Novartis Repeat LFT once or twice in the weekIf elevation persists, establish causality | investigator discretion Monitor LFT within 1 to 4 weeks or at next visit |
| ≤ 1.5 x ULN (patient is asymptomatic) | N/A | Repeat LFT at next visit | |
| Preferred terms | | | |

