| Jaundice | Medically significant | Discontinue the study drug immediately Hospitalize the patient Report to Novartis as an SAE Establish causality | ALT, AST, TBL, Alb, PT, ALP and γGT until resolution ^c (frequency at investigator discretion) |
| "Drug-related hepatic disorders - severe events only" SMQ AE | Medically significant | Discontinue the study drug hospitalization if clinically appropriate Report to Novartis as an SAE Establish causality | Investigator discretion |

^a Elevated ALT/AST > 3 x ULN and TBL > 2 x ULN but with no notable increase in ALP to > 2 x ULN

^b General malaise, fatigue, abdominal pain, nausea, or vomiting, rash with eosinophilia

^c Resolution is defined as an outcome of one of the following: return to baseline values, stable values at three subsequent monitoring visits at least 2 weeks apart, remain at elevated level after a maximum of 6 months, liver transplantation, and death.

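### Two liver-safety rules conflict: whether treatment may be interrupted, and when isolated ALP > 5 x ULN becomes a reportable SAE

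*Protocol*

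**What the plan says.** **Interruption.** Protocol 5.5.5: "Treatment interruptions and dose adjustments of study treatment are" not permitted. A dose not given is to be recorded as a deviation, and no safety exception is stated. Protocol 7.3, for a confirmed liver laboratory trigger, calls for close observation, "including consideration of treatment interruption if deemed appropriate". Section 7.1 lists interruption of study treatment among the actions that may be taken for an adverse event. Section 6.5.6 requires immediate interruption after a positive serum pregnancy test during treatment.

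**SAE status of ALP > 5 x ULN.** In Appendix 2, Table 14-1 places this value under the heading "Medically significant event (SAE", with or without raised bilirubin and with no condition on a repeat test. Table 14-2, in its row for isolated ALP > 5 x ULN, asks for a repeat liver test within 48 hours and then: "If elevation persists, report to Novartis as an SAE Establish causality". Section 7.2.2 requires that "every SAE must be reported to Novartis safety within 24 hours of learning of its occurrence".

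**Stopping and hospitalisation.** For liver events, 7.3 lists "Discontinuation of the investigational drug if appropriate" and qualifies hospitalisation in the same way. Table 14-2 reads "Discontinue the study drug immediately Hospitalize, if clinically appropriate Report to Novartis as an SAE Establish causality" for a potential Hy's Law case and "Discontinue the study drug immediately Hospitalize the patient Report to Novartis as an SAE Establish causality" for jaundice. It also requires immediate discontinuation for ALT/AST > 3 x ULN with symptoms. The list of mandatory stops in 5.6.2 does not refer to Appendix 2.

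**The concern.** Section 7.3 promises a standardised process for liver findings. About 100 sites are to apply it, with no data monitoring committee (8.4) and no adjudication committee (8.5) to even out different readings. The protocol itself links metabolic syndrome to raised risk of non-alcoholic fatty liver disease (1.1), so abnormal liver tests are foreseeable in this population.

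Two things are at stake. A site that pauses treatment because 7.3 invited it to consider doing so has departed from 5.5.5. And an isolated ALP value can be counted as an SAE or not according to the table consulted. The SAP summarises SAEs (core SAP 2.9.1; Extension Period SAP 2.6.1), so the second conflict reaches a reported number.

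**Working it through.** The plan gives no figure to reproduce on this point, so the check is to follow individual results through each rule.

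| Case | One text | Other text | Result |
|---|---|---|---|
| Confirmed ALT 4 x ULN, no symptoms | 7.3: consider interrupting | 5.5.5: interruption not permitted | A site that pauses follows 7.3 and deviates from 5.5.5 |
| Isolated ALP > 5 x ULN, not confirmed on repeat | Table 14-1: SAE on the value | Table 14-2: SAE report only on persistence | 1 SAE against 0 SAE reports |
| Isolated ALP > 5 x ULN, persisting | Table 14-1: SAE from the first value | Table 14-2: report once persistence is shown | SAE under both, but the 24-hour clock starts at different times |
| Potential Hy's Law, symptomatic ALT/AST > 3 x ULN, jaundice | 7.3: stop and hospitalise if judged appropriate | Table 14-2: stop immediately; hospitalisation unqualified for jaundice | The body text is looser than the table |

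**Case 1.** Table 14-2 does not settle the matter. Its row for asymptomatic ALT/AST > 3 to ≤ 5 x ULN lists repeat tests and a causality assessment, and says nothing about interruption. Sections 7.1 and 6.5.6 both provide for interruption, so 5.5.5 is out of step with three other sections.

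**Cases 2 and 3.** Both tables call the event medically significant. They differ on whether the first value or the confirmed value makes it reportable.

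**Rows not relied on.** For ALT/AST > 5 x ULN and isolated bilirubin > 3 x ULN, the layout of Table 14-2 as I could read it does not show whether the SAE report depends on persistence. I draw nothing from those rows about SAE counts.

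**Opportunity.** Table 6-1 has routine chemistry at visits 1, 2, 4 and 6 to 12 in the core study: 1 + 1 + 1 + 7 = 10 panels. Visit 1 precedes treatment and visit 12 follows the last injection at week 24, so at most 10 − 2 = 8 panels can bear on interruption. This counts occasions, not events. The documents give no rate of ALP or transaminase elevation, so no expected number of affected patients or SAEs follows.

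**The case against.** **On stopping, most of the objection stands.** Section 7.3 introduces its list as a summary and refers to Table 14-2 for detail. Appendix 1 also points to Appendix 2 as the place where liver follow-up is specified. Table 14-2 mixes immediate stops, stops on persistence and, for isolated ALP > 5 x ULN, no stop step, so one bullet covering them all has to be conditional. Section 5.6.2 does require stopping for adverse events and laboratory abnormalities that in the investigator's judgment prevent continuation, and for safety risk. A reader might infer that the protocol gives opposite stopping orders for a Hy's Law pattern. The documents do not support that. What remains is loose wording and a missing cross-reference from 5.6.2.

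**On interruption, the objection limits the consequence.** Section 11.1 expects the investigator to take immediate action needed for patient safety even if it is a deviation, and 5.6.2 requires discontinuation when continuing would harm the risk/benefit balance. No site is forced to keep dosing. But a pause that 7.3 itself invites should not need the emergency clause, and the two texts still conflict. Section 6.5.6 is weaker support, because 5.6.2 also lists pregnancy as a reason to discontinue.

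**On the 24-hour rule, a reader might infer that the 48-hour repeat makes SAE reports up to 24 hours late.** That does not follow. The clock in 7.2.2 runs from learning of the SAE. If persistence defines the SAE, it starts at confirmation and nothing is late. In addition, 48 hours is the window for repeating the test, and laboratory turnaround is not stated, so 48 − 24 bounds nothing.

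**On reach.** Both arms receive the same drug under the same liver rules, and SAEs are only summarised. Nothing here shows bias between arms or an effect on PASI 90 at week 28.

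**Conclusion.** Two contradictions stand in the text: 5.5.5 against 7.3 on interruption, and Table 14-1 against Table 14-2 on when isolated ALP > 5 x ULN is a reportable SAE. The wording on stopping and hospitalisation in 7.3 is a lesser point of clarity.

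The demonstrated effect on the SAE count is one event per patient with an isolated ALP > 5 x ULN that does not persist, counted under one table and not the other. It should not be extended to liver SAEs in general. Its total size is unknown. Differing site readings are possible, but without an event rate the documents do not let one call them likely.

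This is an internal inconsistency that should be corrected for consistent safety handling and a well-defined SAE count. It does not threaten the primary analysis. The conclusion assumes that the liver laboratory triggers of 7.3 correspond to the special-interest level of Table 14-1, a mapping the protocol implies but does not state.

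**What to change.** - Reconcile 5.5.5 with 7.3, 7.1 and 6.5.6, so that the protocol gives one answer on whether and when study treatment may be interrupted for safety, and on whether such a pause is recorded as a deviation.
- Make Tables 14-1 and 14-2 agree on whether isolated ALP > 5 x ULN becomes a reportable SAE at the first value or on persistence, and state when the 24-hour period of 7.2.2 then begins.
- State in 7.3 and 5.6.2 that the body text and the Appendix 2 tables form one rule, and name the governing text. Use the same terms in 7.3 and Table 14-1 for the two levels of liver finding.

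The sponsor's safety physicians decide which clinical rule applies; this review takes no position on that. The cost is amendment wording and a notice to sites, with no new assessments, staff or patients. If ALP values have already been handled under both readings, the study report should say which definition the SAE tables use.

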7.4 Reporting of study treatment errors including misuse/abuse

Medication errors are unintentional errors in the prescribing, dispensing, administration or monitoring of a medicine while under the control of a healthcare professional, patient or consumer (EMA definition).

Misuse refers to situations where the medicinal product is intentionally and inappropriately used not in accordance with the protocol.

Abuse corresponds to the persistent or sporadic, intentional excessive use of a medicinal product, which is accompanied by harmful physical or psychological effects.

Study treatment errors and uses outside of what is foreseen in the protocol will be collected in the DAR (dose administration record) eCRF irrespective of whether or not associated with an AE/SAE and reported to Safety only if associated with an SAE. Misuse or abuse will be collected and reported in the safety database irrespective of it being associated with an AE/SAE.

Table 7-1 Guidance for capturing the study treatment errors including misuse/abuse

| Treatment error type | Document in Dose Administration (DAR) eCRF (Yes/No) | Document in AE eCRF | Complete SAE form |
|-------------------------------------|--|-------------------------------|--|
| Unintentional study treatment error | Yes | Only if associated with an AE | Only if associated with an SAE |
| Misuse/Abuse | Yes | Yes, | Yes, even if not associated with a SAE |

